#### 10.1.7 Serious Adverse Events

A serious adverse event (SAE) is any AE that meets one of more of the following criteria:

- Is fatal or life-threatening
- Requires hospitalization or prolongs a current hospitalization
- Results in persistent or significant disability/incapacity
- Is a congenital anomaly
- Requires medical or surgical intervention to prevent one of the above outcomes

If any SAE occurs, the treatment status of the subject(s) may be revealed, as clinically indicated. If a patient discontinues medication use due to an AE, the event will be followed, when possible, until resolution. No interim analysis of safety data is planned because the entire study will be conducted over 2 months. However, the frequency of AEs will be under continuous scrutiny during the trial with comparison to AE rates that have been recorded in published PD drug trials.

##### 10.1.7.1 Serious Adverse Events Reporting

The FDA will be informed of SAEs as soon as possible or within 15 calendar days. In addition, the Investigator will notify the FDA of any unexpected fatal or life-threatening experience associated with the use of the drug as soon as possible, or within 7 calendar days, by telephone or facsimile. When the principal investigator has determined that an SAE requires reporting to the FDA (unexpected and possibly related to study drug), the following actions will be taken:

- Telephone the FDA immediately (day of awareness) in the case of reportable death or life-threatening events.
- Complete FDA Form 3500.
- Send the completed Form 3500 to the FDA (preferably by fax at [name]) within the timelines mentioned above.
- Attach the photocopy of all examinations, medical notes and records related to the SAE and document the dates these were made. For laboratory results, include the laboratory normal ranges. For hospitalizations, Admission H&P, Discharge Summary, Consultative reports, etc. could be very helpful. In the case of a fatal event, provide an autopsy report, when it becomes available.

## **10.2 Efficacy Assessments**

### **10.2.1 OAB-SCS**

The primary outcome measure will be the change in the mean daily Overactive Bladder-Symptom Composite Score (OAB-SCS) from baseline to visit 4. . One of the secondary outcome measures will be the change in the mean daily OAB-SCS from baseline to visit 3. The OAB-SCS requires subjects to record the severity of urgency of each micturition over a 72-hour period as follows: 1 = no urgency (normal voiding); 2 = mild (could postpone voiding for as long as necessary without fear of incontinence); 3 = moderate (could postpone voiding for a short while without fear of leakage); 4= severe (could not postpone, had to rush to the toilet); 5= urgency incontinence (could not make it to the toilet without some leakage). The total score is derived by adding the urgency rating of each micturition over a 72-hour period as recorded in a voiding diary. In this way, the OAB-SCS accounts for both frequency and urgency in OAB, and is therefore a more accurate assessment of OAB than measurements of urgency alone (Starkman 2008). Mean daily OAB-SCS is total 72-hour score divided by 3. For incomplete days, the daily score will be adjusted to equal [(total score for the incomplete day / actual number of hours recorded) x 24 hours] (Zinner 2005).

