## **7.3 Screening (Visit 1)**

Visit 1 is the screening visit. At this clinic visit, patients will provide written, informed consent and be assessed for eligibility (excluding those eligibility criteria requiring completion of the voiding diary). A history of the patient's PD symptoms and LUTS will be taken, and the patient's past medical history will be reviewed. Diagnosis of PD will be confirmed based on UK PD Society Brain Bank criteria (Hughes 1992). Current medication list will be reviewed, and a levodopa-equivalent daily dose will be calculated based on the patient's current PD medication list and on published conversion factors (Tomlinson 2010). Eligible subjects will have a stable PD medication regimen for 4 weeks prior to the screening visit and remain on a stable regimen for the duration of the study. Eligible patients will also not be concomitantly taking any of the prohibited medications, including none of the prohibited bladder medications for at least 14 days prior to the screening visit. The patient's history of medication allergies will be reviewed.

Physical examination will be performed, both a general medical examination including vital signs and a neurological examination. Neurological exam will include MDS-UPDRS part 3 evaluation and modified Hoehn and Yahr (HY) staging of PD (Goetz 2004). Post-void residual (PVR) will be assessed. Laboratory testing will include CBC, CMP, and urinalysis (U/A) by dipstick with reflex to urine culture if positive. Pre-menopausal women will have urine hCG measured.

The voiding diary will be dispensed to the patient and training will be provided on how to complete the diary, including instruction on how to measure void volume. The PowerPoint presentation of pelvic floor exercises will also be shown to the patient and each patient will be provided a copy to take home.

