## **7.4 Baseline-(Visit 2) -Treatment Initiation**

### **7.4.1 Confirmation of Eligibility**

Patients who are deemed eligible in the screening visit will go home to complete a 72-hour voiding diary and return for Visit 2 within 7-14 days after Visit 1. At visit 2, final eligibility will be confirmed by a review of the voiding diary. Subjects eligible to continue will have urinary urgency as evidenced by at least 8 episodes of urgency scores of 2 or greater in 72 hours AND will have urinary frequency as evidenced by having EITHER 8 or more episodes of micturition per 24 hours averaged over 72 hours OR 2 or more episodes of urinary incontinence in 72 hours. In addition to confirming eligibility, the diary scoring will provide the baseline values of mean daily OAB-SCS, number of micturitions per 24 hours, number of incontinence episodes per 24 hours, and mean volume per micturition.

In addition to the diary review, medications will be reviewed again to ensure stability of the PD medication regimen and absence of any prohibited medications. Vital signs will again be measured. At any visit, if a patient is found to have systolic blood pressure over 165, diastolic blood pressure over 100 or heart rate over 100, he or she will be withdrawn from the study.

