#### **7.4.3 Phone visit 1**

Phone visit 1 will take place 28-32 days after Visit 2 and no less than 72 hours prior to Visit 3. Patients will be prompted to resume the voiding diary for 72 hours. Screening for AEs will also take place during this phone visit.

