#### **7.5 Treatment titration**

##### **7.5.1 Visit 3**

Visit 3 will occur 32-40 days after Visit 2. This visit will include the same assessments as Visit 2, including review and entry of data in the voiding diary (mean daily OAB-SCS, number of micturitions per 24 hours, number of incontinence episodes per 24 hours, and mean volume per micturition). Visit 3 will also include review of current medication list, measurement of vital signs, PVR, OAB-q, NMSS, PPBC, and SGI-C. Screening for AEs will also take place during this visit. This will include assessment of symptoms of urinary tract infection and if, in the opinion of the study physician, urinalysis is indicated, dipstick will be performed with reflex to urine culture if positive. In pre-menopausal women, screening for pregnancy risk will be performed and if, in the opinion of the study physician, pregnancy testing is indicated, urine hCG will be measured.

In addition, at Visit 3, all patients who have tolerated mirabegron 25 mg daily or matching placebo (no adverse events on this dose) will be up-titrated to mirabegron 50 mg daily (for those in the active drug arm) or matching placebo (for those in the placebo arm). This will be dispensed as two 25-mg tablets or, for those in the placebo arm, two placebo tablets. Only

those without any AE on 25 mg daily or matching placebo will be eligible to increase the dose.

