### **8.3 Removal of Patients from Study**

A patient will be considered to have completed the study when he or she has completed all study visits through the final visit. Every patient has the right to discontinue study participation at any time at his/her own request, or may be withdrawn at any time at the discretion of the investigator for safety, behavioral, or administrative reasons. Criteria for early termination include, but are not limited to, < 36 hours of time covered in a bladder diary, poor adherence to study medication (less than 70% of study medication consumed), loss of health insurance coverage, and safety issues related to study-related or non-study related adverse events.

If a patient has a clinical necessity to alter their standard PD medications, the patient will be withdrawn from the trial so that changes may be made, except that occasional additional doses of carbidopa/levodopa will be allowed if needed to address periodic worsening of parkinsonian symptoms. Additional doses of carbidopa/levodopa taken during the 72-hour diary periods will be recorded in the diary. If a patient is withdrawn due to an adverse event, the event will be followed, when possible, until resolution. Patients who withdraw from the study may be replaced, but withdrawn patients will not be re-entered into the study.

All data generated up to the time of discontinuation from the study will be analyzed and the reason(s) for discontinuation will be recorded.

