### **10.2.2 Voiding Diary**

In addition to the OAB-SCS, the voiding diary will be used to record number of micturition episodes per 24h, number of incontinence episodes per 24h, and volume per micturition. The change in these variables from baseline to visit 3 and from baseline to visit 4 will be secondary outcome measures. (The voiding diary will also record frequency of Kegel exercises and PRN doses of carbidopa/levodopa, but these will be controls, not outcome measures.)

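### The OAB-SCS scoring rule in section 10.2.1 (fixed divisor of 3, proration by hours) gives no usable score for a diary day with no recorded hours, and section 8.3 does not exclude such diaries

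*Protocol*

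**What the plan says.** The primary endpoint is the change in mean daily OAB-SCS from baseline to Visit 4. Section 10.2.1 adds the urgency ratings of all voids over 72 hours and then fixes the divisor: "Mean daily OAB-SCS is total 72-hour score divided by 3". The synopsis and sections 6.1 and 7.1 repeat the average over three days. Section 10.2.1 also has a rule for partial recording: "For incomplete days, the daily score will be adjusted to equal" that day's score divided by the hours recorded, times 24.

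Section 8.3 gives examples of grounds for early termination in a list it describes as non-exhaustive. The only one that concerns diary coverage is "< 36 hours of time covered in a bladder diary". It sets no minimum per day. The same section says that data collected before discontinuation will be analysed, and section 11.2 specifies an intent-to-treat analysis.

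Several provisions support complete diaries. At screening "training will be provided on how to complete the diary" (7.3), and being willing and able to keep the diary is an inclusion criterion (8.1). At the first phone visit "Patients will be prompted to resume the voiding diary for 72 hours" (7.4.3), and 7.5.2 does the same before Visit 4. The diary is checked for eligibility at Visit 2 (7.4.1), and Visits 3 and 4 include "review and entry of data in the voiding diary" (7.5.1, 7.6). None of these says how to score a day left blank.

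**The concern.** The proration in 10.2.1 exists so that unrecorded time does not count as symptom-free time. It does this only when a day has at least some recorded hours. On a blank day it has nothing to scale, while the divisor stays at 3. The analyst must then choose between no value, a total that treats the blank day as zero, and a divisor other than the stated one.

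This is the scoring rule of the only primary endpoint, and section 11.5 makes the claim of superiority depend on that endpoint. If a blank day adds nothing, one at Visit 4 looks like improvement and one at baseline looks like worsening. If the choice stays open, it could be made after the data have been seen.

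**Working it through.** **Inputs.** The divisor of 3 and the proration (day score / hours recorded × 24) are from 10.2.1. The 36-hour limit is from 8.3. The protocol gives no OAB-SCS level, so a true mean of 33 per day is assumed. With equal days and a constant hourly rate, the percentage error does not depend on that level. The protocol states no figure of its own to reproduce here.

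**Which diaries are affected.** One blank day leaves at most 48 hours, so the diary can reach 36 hours or more. Two blank days leave at most 24 hours and meet the termination criterion.

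**Literal rule on a blank day.** 0/0 × 24 is undefined, so there is no score.

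**Blank day adds nothing, divisor stays 3, compared with dividing by days that have hours:**

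| Hours per day | Sum of daily scores after proration | Divided by 3 | Divided by days with hours |
|---|---|---|---|
| 24+24+0 | 33 + 33 = 66 | 22 (−33.3%) | 66/2 = 33 |
| 24+12+0 | 33 + (16.5/12 × 24 = 33) = 66 | 22 (−33.3%) | 66/2 = 33 |
| 12+12+12 | 33 + 33 + 33 = 99 | 33 | 33 |

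The last row is right because the hourly rate is assumed constant over the unrecorded hours.

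**Unequal days, same mean of 33, one day blank:**

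- True days 30, 33, 36. Fixed 3: 69/3 = 23, 66/3 = 22 or 63/3 = 21 (−30.3% to −36.4%), average 22. By days with hours: 34.5, 33 or 31.5, average 33.
- True days 24, 33, 42. Fixed 3: 75/3 = 25, 66/3 = 22 or 57/3 = 19 (−24.2% to −42.4%), average 22. By days with hours: 37.5, 33 or 28.5 (+13.6% to −13.6%), average 33.

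On the zero reading the score is too low whichever day is blank. Dividing by days with hours is right on average and misses only through day-to-day variation.

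**What one patient would do.** An unchanged patient with a complete baseline and one blank day at Visit 4 would show 22 − 33 = −11 on the zero reading. With 20 per arm, that moves the arm mean by 11/20 = 0.55.

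**Limit on the baseline case.** The frequency criterion in 7.4.1 is "8 or more episodes of micturition per 24 hours averaged over 72 hours". If the 72-hour average is also taken literally, 8 voids on each of two recorded days give 16/3 = 5.3 per 24 hours, which fails. Entry with one blank day would need 24 voids in 48 hours, or 12 per recorded day, unless the subject qualifies through two incontinence episodes.

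**The case against.** The strongest reply is that handling a wholly missing day is missing-data detail for the statistical analysis plan, which is not at hand. On this view the fixed 3 is right for a full 72-hour total, the proration is right for a partly recorded day, and neither sentence claims to cover a blank one. An undefined result would also stop the calculation and force a decision, whereas the one-third error needs a reading that goes against the purpose of the proration. This carries weight and is a reason to grade the point low. It does not remove the point: the protocol itself fixes both the divisor and the formula, and together they fail on foreseeable data. A plan that copies 10.2.1 inherits the gap; one that changes the divisor departs from the protocol's definition of the endpoint.

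Four stronger readings are tempting, and the protocol does not support them:

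- *That section 8.3 approves such diaries.* It is a non-exhaustive list of grounds for withdrawing patients, not a rule on which diaries are valid, and the investigator may withdraw a patient above 36 hours. It only fails to exclude them. Equally, because data before discontinuation are analysed, 36 hours does not decide which diaries are scored.
- *That every incomplete diary is mis-scored.* Diaries with some hours on each day do not have this error, subject to the constant-rate assumption. Recording only in waking hours would strain that assumption, which is a separate weakness of the proration.
- *That the treatment comparison is biased.* Allocation is randomized and blinded (9.3), and nothing in the protocol suggests that blank days would differ by arm.
- *That the secondary diary counts have the same faulty formula.* Section 10.2.2 lists "number of micturition episodes per 24h, number of incontinence episodes per 24h" but states no divisor, so it contains no formula to correct.

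The diary form in Appendix 14.2 appears only as a heading in the text available, and it may define diary days or completion rules. That limits confidence.

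**Conclusion.** The point stands as a minor defect in a stated primary-endpoint rule. For a diary with one blank day, 10.2.1 gives either no value or, if the day adds nothing, a score one third too low (22 against 33 under equal days and a constant rate; −24% to −42% when the days are 24, 33 and 42). The second reading is probably not intended.

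At trial level the likely effect is extra noise and slight shrinkage of any difference, with bias only if blank days differ by arm. Its size cannot be given: the protocol states no blank-day rate and no standard deviation, and training, prompts and diary review should make blank days uncommon. The figure of 0.55 per affected patient is arithmetic on an assumed score, not an estimate of what will happen.

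**What to change.** In 10.2.1, before unblinding, replace the fixed divisor with a sentence to this effect:

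> The mean daily OAB-SCS is the sum of the daily scores, with incomplete days prorated as already stated, divided by the count of diary days that have any recorded hours. A diary without recorded hours is missing.

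Complete diaries score exactly as before, and the cited proration stays. The cost is one sentence and one line of programming. Using the same denominator for the 24-hour counts in 10.2.2 would be sensible for consistency, but it corrects nothing stated there.

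There are two downsides. A two-day score is less precise than a three-day score: if days are independent, the variance rises by (1/2)/(1/3) = 1.5 and the standard deviation by √1.5 = 1.22. And very short recorded days are still extrapolated: one recorded hour with a single void rated 4 becomes 4/1 × 24 = 96, so with two days at 33 the score is (33 + 33 + 96)/3 = 54, or 64% above 33. The existing rule already does this, and the new sentence does not cure it.

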### **10.2.2 Voiding Diary**

In addition to the OAB-SCS, the voiding diary will be used to record number of micturition episodes per 24h, number of incontinence episodes per 24h, and volume per micturition. The change in these variables from baseline to visit 3 and from baseline to visit 4 will be secondary outcome measures. (The voiding diary will also record frequency of Kegel exercises and PRN doses of carbidopa/levodopa, but these will be controls, not outcome measures.)

### **10.2.3 OAB-q**

The Overactive Bladder questionnaire symptom severity scale (OAB-q) measures the impact of bladder symptoms by asking patients to rate the severity of eight OAB symptoms on a 6-

point scale. The questionnaire has been validated for use in the general population (Coyne 2002) and in patients with Parkinson disease (Iacovelli 2010).

#### **10.2.4 NMSS**

The NMSS is a validated rating scale of non-motor symptoms in Parkinson disease (Chaudhuri 2007). It rates the severity and frequency of 30 symptoms in 9 domains, including 3 symptoms of overactive bladder. The other domains it evaluates are cardiovascular, sleep/fatigue, mood/cognition, perceptual problems/hallucinations, attention/memory, gastrointestinal, sexual function, and miscellaneous (pain, sense of smell, change in weight, and excessive sweating). Severity is rated from 0 (none) to 3 (major source of distress) and frequency is rated from 1 (rarely, <1/week) to 4 (very frequent, at least daily). The score on each item is the product of the severity and frequency ratings. The total score for the NMSS is the sum of all item scores.

#### **10.2.5 PPBC**

The PPBC asks patients to rate the severity of their bladder symptoms on a 6-point scale, from “My bladder condition does not cause me any problems at all” to “My bladder condition causes me many severe problems.” This single-item, global measure has been validated for use in a general population with OAB (Coyne 2006).

#### **10.2.6 SGI-C**

The Subject’s Global Impression of Change will be assessed by asking a single question at visit 3 and visit 4.: “Since starting the study drug, how have your bladder symptoms changed?” Answers will be on a 7-point scale: 1 = much improved; 2 = somewhat improved; 3 = minimally improved; 4 = no change; 5 = minimally worse; 6 = somewhat worse; and 7 = much worse.

## **11. DATA MANAGEMENT AND STATISTICAL ANALYSIS**

Statistical analysis will be performed by a consulting statistician contracted with EvergreenHealth.

### **11.1 Sample Size Considerations**

This is a prospective, double-blinded, randomized controlled pilot study. The purpose is to test a hypothesis in a preliminary fashion and to assess for safety in this population with a specific neurological disease. As such, a power calculation may be irrelevant. However, a small number of subjects (e.g. less than 10) may cause significant sampling error to miss a treatment effect or common safety issue. Some entities that establish criteria for level of evidence consider a sample size of 20 subjects in each arm to be a minimum representative population to be considered for Class III or better classification of Level of Evidence. Therefore, a sample size of 40 subjects is a reasonable number for a pilot study of this nature.

## 11.2 Study Population

The study population will include all patients who pass screening and undergo randomization. Data will be analyzed in an intent-to-treat fashion.

## 11.3 Baseline and Demographic Characteristics

The following characteristics will be summarized descriptively for placebo and drug groups:

- Demographics (age, gender, race)
- Parkinson disease characteristics at baseline (disease duration, date of onset, initial symptom, PD type [tremor-dominant or akinetic-rigid], modified Hoehn and Yahr stage in the ON state, and MDS-UPDRS part 3 score in the ON state)
- Levodopa-equivalent daily dose (LEDD)
- Other medications used for OAB

## 11.4 Safety Analysis

AEs will be summarized by treatment group (study drug or placebo) and by dose. Changes in vital signs (BP, HR, RR) and changes in post-void residual will be analyzed to detect differences between active drug and placebo.

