## **9.2 Investigational drug**

The study medication and matching placebo will be provided by Astellas. The active medication will be mirabegron 25 mg po daily from Baseline Visit (Visit 2) to Titration Visit (Visit 3). At the Titration Visit, all patients who have tolerated mirabegron 25 mg daily (no adverse events on this dose) will be up-titrated to mirabegron 50 mg daily. This will be dispensed as two 25-mg tablets or, for those in the placebo arm, two placebo tablets. Only those without any AE on 25 mg daily or matching placebo will be eligible to increase the dose. The research pharmacist will dispense the active or placebo medication at randomization and again at the Titration Visit. An extra 5-day supply of medication will be provided for each study period to allow a window for scheduling of appointments.

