#### 10.1.6 Adverse Events

*Subjects will be monitored for adverse events throughout the trial. The occurrence of adverse events will be ascertained by observation, telephone monitoring and questioning by the investigator. Safety assessments will consist of monitoring and recording all adverse events, including serious adverse events.*

An adverse event (AE) is any symptom, physical sign, or medical condition that emerges during the study or, if present at screening, worsens during the study, regardless of the suspected cause. Adverse events include adverse drug reactions, illness with onset during the study, exacerbations of pre-existing conditions or clinically significant changes in physical examination or significantly abnormal objective test findings. Medical conditions/diseases present before starting study treatment are only considered adverse events if they worsen after starting study treatment. All adverse events will be recorded and graded as mild, moderate or severe by the principal investigator in accordance with general guidelines of clinical research, outlined here:

- **MILD:** An event that causes transient or minimal symptoms and that does not interfere with daily activities.
- **MODERATE:** An event that causes symptoms sufficient to interfere with but not prevent daily activities.
- **SEVERE:** An event that prevents normal, everyday activities.

Adverse events will also be classified by their relationship to the study medication by the principal investigator in accordance with general guidelines of clinical research, outlined here:

- **Definitely Unrelated:** The AE is definitely not related to the drug. This designation is reserved for those events that do not follow a reasonable temporal sequence following drug administration (e.g. occur prior to study treatment) or for those events that cannot be even remotely related to study participation.

- **Unlikely related:** There is no reasonable association between the study treatment and the suspected event and the event could have been produced by the patient's clinical state or other therapy administered to the patient.
- **Possibly related:** The suspected AE may or may not follow a reasonable temporal sequence from study treatment administration but seems to be the type of reaction that cannot be dismissed as unlikely. The event could have been produced or mimicked by the patient's clinical state or other therapy administered to the patient.

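### The adverse-event summary by dose sets an AE-free subset on 50 mg against all active subjects on 25 mg, so it cannot be read as a dose comparison

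*Protocol*

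**What the plan says.** Section 11.4 of the protocol fixes the safety tabulation: "AEs will be summarized by treatment group (study drug or placebo) and by dose". It names no period, denominator or exposure adjustment for the dose split.

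The dose a subject takes after Visit 3 depends on what happened before it. Under Section 9.2 every subject randomised to active drug takes 25 mg from Visit 2 to Visit 3, and then "Only those without any AE on 25 mg daily or matching placebo will be eligible to increase the dose". Section 7.5.1 repeats the rule. Section 10.1.6 defines an AE broadly, as anything that "emerges during the study or, if present at screening, worsens during the study, regardless of the suspected cause", so an event unrelated to the drug also blocks the step.

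The placebo arm goes through the same step: "This will be dispensed as two 25-mg tablets or, for those in the placebo arm, two placebo tablets". Section 11.1 gives as one of the trial's purposes "to assess for safety in this population with a specific neurological disease".

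**The concern.** The titration rule assigns subjects to dose strata by their AE history, and AEs are what the table then counts. The 50 mg stratum holds only subjects who had no AE in the first period, observed in the second. The 25 mg stratum holds all active subjects in the first period, plus later time on 25 mg from subjects who had an AE and stayed on drug. A first-period AE is counted at 25 mg and also keeps that subject out of the 50 mg row.

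A reader who sets the two rows side by side sees dose, selection and time on study combined. If some subjects are more AE-prone than others, or if AEs cluster soon after starting, the 50 mg rate will tend to read low. Safety is a stated purpose, and in a 40-subject pilot the descriptive AE tables are most of the safety evidence. This is also the only stated AE summary that isolates 50 mg.

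**Working it through.** The protocol gives no AE rate and no by-dose calculation, so there is no figure to reproduce. The check asks what the by-dose table would show if 25 mg and 50 mg had the same true AE rate.

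**Inputs from the protocol**
- First period: "Visit 3 will occur 32-40 days after Visit 2" (Section 7.5.1).
- Visit 4 is 74-82 days after Visit 2 (Section 7.6), so the second period lasts 74 − 40 = 34 to 82 − 32 = 50 days.
- 20 subjects on active drug (synopsis).

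**Assumed inputs (not in the documents)**
- Periods of 35 and 42 days, inside those windows.
- First-period AE risk p = 30% to 50%.
- Between-subject variation in AE rate: gamma frailty with mean 1 and variance θ = CV², CV 0.5 to 1.0.

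**Formulas**
- Cumulative first-period hazard: H = [(1 − p)^(−θ) − 1]/θ. The probability of staying AE-free is S(H) = (1 + θH)^(−1/θ) = 1 − p.
- Mean relative AE rate of those who pass to 50 mg: m = 1/(1 + θH).
- Contribution of those who had an AE: a = 1 − (1 − p)m.
- Mean relative rate on 25 mg if all of them stay on drug: r = (35 + 42a)/(35 + 42p).
- Event-rate ratio, 50 mg to 25 mg: m/r.
- Crude percentage with an AE on 50 mg: 1 − S(H + 1.2H)/S(H), where 1.2 = 42/35. On 25 mg it is p.

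**Two corners worked through**
- p = 0.30, CV 0.5 (θ = 0.25): H = 0.373, m = 0.915, a = 1 − 0.70 × 0.915 = 0.360. Then r = (35 + 15.1)/(35 + 12.6) = 1.053, and the rate ratio is 0.915/1.053 = 0.87. Percentages: 32.3% on 50 mg against 30%, ratio 1.08.
- p = 0.50, CV 1.0 (θ = 1): H = 1, m = 0.50, a = 1 − 0.50 × 0.50 = 0.75. Then r = (35 + 31.5)/(35 + 21) = 1.188, and the rate ratio is 0.50/1.188 = 0.42. Percentages: 1 − (2/3.2) = 37.5% against 50%, ratio 0.75.

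**Results with no true dose effect**

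| First-period AE risk | CV | Up-titrated, of 20 | Event-rate ratio 50/25 mg | Ratio of crude percentages |
|---|---|---|---|---|
| 30% | 0.5 | 14 | 0.87 | 1.08 |
| 30% | 1.0 | 14 | 0.59 | 0.88 |
| 50% | 0.5 | 10 | 0.79 | 1.01 |
| 50% | 1.0 | 10 | 0.42 | 0.75 |

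**Sensitivity**
- CV 0: the event-rate ratio is 1.00. CV 0.25: 0.94-0.96.
- If every subject with a first-period AE is off drug in the second period, the 25 mg rate is 1 and the ratio is m, which is 0.50 to about 0.91.
- If the true rate at 50 mg is 1.5 times that at 25 mg, the event-rate ratio reads 1.5 × 0.42 = 0.63 to 1.5 × 0.87 = 1.30.

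**Would stepped-up mirabegron against stepped-up placebo solve it?** Take a true hazard ratio of 1.5 in both periods, θ = 1, placebo risk 30% and equal periods, so H is 0.4286 on placebo and 0.6429 on drug.
- First period: drug risk 1 − 1/1.6429 = 39.1%, risk ratio 39.1/30 = 1.30.
- Second period, AE-free subjects only: drug 1 − 1.6429/2.2857 = 28.1%, placebo 1 − 1.4286/1.8571 = 23.1%, risk ratio 1.22.

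The gate removes more AE-prone subjects from the drug arm than from placebo, so this comparison is also pulled towards no difference. Keeping all subjects in their randomised arm avoids that.

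**The case against.** Section 11.4 plans a summary. It does not plan a contrast or test of 50 mg against 25 mg, and its wording could mean arm crossed with dose step, since placebo has a matching step. Denominators and exposure adjustment are commonly left to an SAP, which is not shown. This limits the point to how the table will be read. It does not remove it: the protocol itself fixes both the selection rule and the dose split, and even in an arm-by-dose layout the 25 mg and 50 mg cells of the active arm are not comparable.

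The size is also open to challenge. Every rate and CV above is assumed. With 20 active subjects, a single trial's event-rate ratio would vary widely: the 95% sampling range is about 0.17-2.9 at 30% risk and CV 0.5, and about 0.07-1.16 at 50% risk and CV 1.0. Outside the extreme case the bias lies well inside that noise. That stands, and it is why no particular figure should be expected in the data.

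Four stronger readings are tempting, and the documents do not support them:
- **That 50 mg will necessarily look safer.** This needs subjects to differ in AE-proneness or AEs to cluster early. With crude percentages, the longer second period assumed here can cancel the effect.
- **That every subject with an AE stays on 25 mg.** Section 8.3 allows withdrawal for AEs, and Sections 10.1.2 and 10.1.5 stop study medication on vital-sign and post-void residual limits.
- **That the by-dose table is the only planned look at 50 mg.** Section 11.4 also compares vital signs and post-void residual between arms, and both are measured at Visit 4, after titration.
- **That stepped-up drug against stepped-up placebo is a fair comparison.** Both groups are selected after randomisation, as worked above.

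**Conclusion.** The point holds as a fault in a stated analysis choice. The by-dose AE summary confounds dose with selection on prior AEs and with time on study, so it cannot inform relative tolerability of 25 mg and 50 mg. The likely direction is to understate AE rates at 50 mg, conditional on heterogeneity between subjects or early clustering of AEs. Both are plausible, and neither is documented.

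Under the assumed ranges and no dose effect, the event-rate ratio is about 0.42-0.87 and the ratio of crude percentages about 0.75-1.08. Section 11.4 does not say which measure will be shown, so even the direction of the table depends on an unstated choice. The whole-trial AE summary by randomised arm and the efficacy analysis are not affected. The change should be made, but it does not threaten the trial's main conclusions.

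**What to change.** In Section 11.4, replace the words *and by dose* with AE summaries by randomised arm within period, each with exposure time:

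- (a) Visit 2 to Visit 3: all subjects, mirabegron against placebo.
- (b) Visit 3 to Visit 4: all subjects in their randomised arm, whether or not they stepped up. This is the main second-period comparison. It describes the titration regimen as delivered, not 50 mg alone.
- (c) As supplementary description only: stepped-up and not-stepped-up subjects in each arm, labelled as groups selected after randomisation.

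Add one sentence saying that 25 mg and 50 mg AE rates within the active arm are not to be read as a dose comparison.

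The cost is a short edit and a small re-cut of tables from data already collected. The titration rule is unchanged. No design yields an unselected estimate for 50 mg alone while that rule stands, and the report should say so.
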